Background: People with intellectual disabilities experience greater digital exclusion and have poorer health literacy. In the absence of good quality research, health inequalities are likely to worsen leading to poorer health outcomes. Research is needed to better understand digital health participation in people with intellectual disabilities. Via the creation of a valid measure, this investigation will identify the predictors, outcomes and experiences of digital health participation and exclusion among adults with intellectual disabilities.

Primary Aim: To determine levels of digital health participation and inequality among adults with intellectual disabilities.

Secondary Aims: (i) To co-create and produce a digital health participation scale for use with people with intellectual disabilities and their carers; (ii) To identify influences, consequences and support needs of people with intellectual disabilities in their digital health participation; (iii) To longitudinally model factors affecting digital health participation and wellbeing of people with intellectual disabilities; (iv) To determine levels of digital health inequality by comparing digital health participation between people with intellectual disabilities and a referent group of non-disabled people; (v) To explore processes of everyday digital health participation; (vi) To develop interventions to enhance digital health participation of people with intellectual disabilities.

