1.2. Theoretical Framework

People diagnosed with intellectual disabilities are cognitively, genetically and clinically extremely heterogeneous (e.g. Maia *et al.*, 2021; Sajewicz-Radtke *et al.*, 2022). People with intellectual disabilities with more severe and profound levels of cognitive impairment will need greater support to engage with all aspects of life, including healthcare, information and communication technologies (ICT), and research (APA,2013). Similarly, the intersection of

intellectual disability with other characteristics including ethnicity, mental and physical health conditions, advancing age, residential and financial circumstances etc. can also exacerbate social and health exclusion and exclusion from research (Dhamoon & Hankivsky, 2011). To enable full consideration of digital health participation across the population of people with intellectual disabilities strategic research recruitment should be enacted to incorporate heterogeneity and intersectionality (NIHR, 2020; NIHR, 2022).

This study takes a strengths-based approach to digital health participation (Niemiec *et al.*, 2017), to understand the demands of digital health environments that people with intellectual disabilities encounter. In addition, self-determination theory (Deci & Ryan, 1985), a theory of intrinsic motivation which posits that humans are motivated to engage in activities where they experience mastery, autonomy and a sense of relatedness (Wehmeyer, 2020a), is the primary theoretical lens underpinning the study. Self-determination has been strongly linked to quality of life and wellbeing in people with intellectual disabilities (Wehmeyer, 2020b). Teaching of skills related to self-determination has been linked to the achievement of desired outcomes for people with intellectual disabilities (Wehmeyer, 2020a). It is essential that the self-determination of people with intellectual disabilities in relation to digital health participation is enhanced and better understood. Through better understanding of experiences of mastery, autonomy and interactions pertaining to digital literacy and health participation, interventions to support digital health participation can be devised.

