People with intellectual disabilities are more likely to experience both digital exclusion (Chadwick *et al.*, 2022; Alfredsson Ågren *et al.*, 2020) and lower levels of health literacy (20). The digital inclusion (16) and health literacy (Latteck & Bruland, 2020; Geukes *et al.*, 2018; Sørensen *et al.*, 2012) of people with intellectual disabilities are influenced by individual (e.g. cognitive, literacy, understanding, self-awareness), interpersonal (e.g. support, communication, education), contextual and societal (e.g. accessibility, residence, employment, finances, attitudes) factors. Taken together, digital inclusion and health literacy demonstrate how effectively people with intellectual disabilities can participate in decisions about their own health. Health literacy refers to the motivation, knowledge, appraisal and application of health information to make healthcare decisions (Vetter *et al.*, 2021). It influences health behaviour, is associated with positive healthcare outcomes, and is a pre-requisite for patient empowerment (Berkman *et al.*, 2011; Crondah & Karlsson, 2016; Chinn, 2014). Measures of health literacy have thus far not adequately considered the experiences of people with intellectual disabilities (Latteck & Bruland, 2020; Chinn, 2014) or the utilisation

of health-related information and communication technologies (ICT) for this population (Sørensen *et al.*, 2012).

Health participation has been highlighted as challenging to define but has been defined as being involved in performing societally expected roles within certain health related domains (Eyssen *et al.*, 2011). Within health participation the expectation for performance is influenced by and impacted on by levels of health literacy, as defined above, and includes health behaviours (e.g. physical activity, maintenance of a healthy diet moderation, abstinence of alcohol intake etc.) (Berkman *et al.*, 2011; Sørensen *et al.*, 2012). More widely, it incorporates processes of engagement with health-related provision and negotiating support (health and dental check-ups and use of primary and tertiary healthcare) (Sørensen *et al.*, 2012; Eyssen *et al.*, 2011; Rifkin, 2014).

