provided in the manual with individualised support offered by RAs and co-researchers on an as needed/requested basis. The manual will provide guidance on deciding whether independent completion, supported completion or, proxy completion is most appropriate. The survey digitally housed (Qualtrics), printed versions of the survey will also be available if requested for subsequent entry by RAs. Carers proxy completing the survey will also be offered the same range of completion options (Paper-based, online completion (housed on Qualtrics), telephone completion, face-to-face completion as an interview with a researcher).

The survey will comprise: (i) The Digital Health Participation Survey developed in WP1; (ii) General ICT Use and Access (Anrijs *et al.*, 2022); (iii) Physical and Mental Wellbeing (EQ-5-3L, (Herdman *et al.*, 2011)); (iv) Salient Demographic (Gathered from participants in accordance with PROGRESS-plus criteria) (Oliver *et al.*, 2008; O'Neill *et al.*, 2014) and Background information (Current and historical health conditions, ongoing health involvement, day activities, levels of support need, literacy and communication, level of cognitive impairment and postcode to enable gathering of deprivation indices).

Longitudinal survey statistical analysis

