2.4.2 Comparative study of Digital Health Inequality

A cross sectional comparative study will contrast digital health participation of people with intellectual disabilities to a reference group people without disabilities.

Comparator

A reference group of 200 participants without disabilities will be recruited across the study sites via local advertisement and social media. This referent group will concurrently complete the same Digital Health Participation survey online via Qualtrics. A referent sample of 200 will allow detection of a group difference, $d=0.2812$ (small-medium effect) at 90% power, 2:1 group ratio, and $\alpha=0.05$. Sample size calculations were conducted using G*Power 3.1.9.7. Our overall planned accrual rate for the referent group is 25-30 participants per month across the four study sites (6-8 per site) over seven months to reach our aim of a final sample size of 200.

Primary outcome

Digital health participation levels as developed from the work in WP1 will be used as the primary outcome measure.

Secondary outcome

Level of mental and physical wellbeing will be measured using the EQ5 (Herdman *et al.* 2011).

Comparative study statistical analysis

Descriptive analysis of levels and frequency of digital health participation of the groups (N=600). Between group comparison using general linear model (GLM) of digital health participation of people with intellectual disabilities.

The study will use propensity score weighting (inverse probability weights) to reduce the bias due to confounding variables and ensure sufficient balance across groups. The propensity scores will be generated on the basis of the following variables: geographic region, sex, age band, ethnicity, and deprivation index. In the event that models including the probability weights do not converge, we will explore other approaches to resolve (i.e. direct adjustment as the number of covariates is relatively small).

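### The only tested comparison weights on area deprivation, so it estimates the gap at equal deprivation, while the stated aim is the level of inequality; the contrast should be shown with and without deprivation in the weights

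*Protocol*

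**What the plan says.** The secondary aim that the comparison serves, given in the Research Summary, is "To determine levels of digital health inequality by comparing digital health participation between people with intellectual disabilities and a referent group of non-disabled people". The primary aim is of the same kind: "To determine levels of digital health participation and inequality among adults with intellectual disabilities". Neither carries a condition about equal deprivation.

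Section 2.4.2 then fixes the analysis. A general linear model compares the groups, with inverse probability weights whose purpose is "to reduce the bias due to confounding variables and ensure sufficient balance across groups". On their content it says: "The propensity scores will be generated on the basis of the following variables: geographic region, sex, age band, ethnicity, and deprivation index". If the weighted models do not converge, the example given of another approach is "direct adjustment as the number of covariates is relatively small". No other covariate set is named, so that route would presumably also condition on deprivation. The only other group comparison in the section is a descriptive analysis of both groups (N=600).

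Section 2.4.1 shows where the index comes from: the survey collects "postcode to enable gathering of deprivation indices". Section 1.2 places socioeconomic circumstances among the influences on digital inclusion and health literacy, naming "contextual and societal (e.g. accessibility, residence, employment, finances, attitudes) factors", and adds that "residential and financial circumstances etc. can also exacerbate social and health exclusion and exclusion from research".

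**The concern.** Region, sex, age band and ethnicity are not consequences of intellectual disability in any sense that the protocol's framework suggests. Deprivation may be different. An adult's current postcode comes later in life than the disability, and the framework treats where people live and what they can afford as part of how exclusion arises. If intellectual disability leads to living in a more deprived area, and living there lowers digital health participation, then deprivation lies on the route from disability to the outcome. Weighting the groups to the same deprivation treats that route as confounding and takes it out.

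The null hypothesis of the weighted model is then no difference between equally deprived people, which is not the same as no inequality. At stake is what the headline figure means. A gap that runs partly through deprivation would be reported as smaller than it is, and one that runs wholly through it would be weighted to about zero, with nothing in the plan to say that the estimate is conditional on deprivation.

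**Working it through.** **Inputs from the protocol (sections 2.4.1 and 2.4.2).** 400 people with intellectual disabilities, 200 referents, detectable difference d=0.2812, power 90%, alpha 0.05 (sidedness not stated).

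**Reproducing the plan's figure.** Two-sample t test, noncentrality = d / √(1/200 + 1/400) = 0.2812 / 0.0866 = 3.247. Noncentral-t power, two-sided at 0.05, is 0.900, and the detectable d at 90% power is 0.2812. A one-sided test would give power 0.945 and d=0.254, so the stated figure is two-sided. It is correct as an unweighted calculation without covariates. No numerical error is alleged.

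**What weighting on deprivation does.** Let D be the total gap in SD units of the outcome, s the group difference in deprivation in SD, and b the fall in the outcome per SD of deprivation. The gap at equal deprivation is D − s × b. The protocol gives neither s nor b. The values below are assumptions (s from 0.2 to 0.5, b from 0.1 to 0.3), and power uses the t test above at 400:200.

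| D | s | b | removed (s × b) | share of D | gap left | power |
|---|---|---|---|---|---|---|
| 0.2812 | 0 | any | 0 | 0% | 0.281 | 90.0% |
| 0.2812 | 0.2 | 0.1 | 0.02 | 7% | 0.261 | 85.3% |
| 0.2812 | 0.3 | 0.2 | 0.06 | 21% | 0.221 | 72.2% |
| 0.2812 | 0.5 | 0.2 | 0.10 | 36% | 0.181 | 55.1% |
| 0.2812 | 0.5 | 0.3 | 0.15 | 53% | 0.131 | 32.8% |
| 0.5 | 0.2 | 0.1 | 0.02 | 4% | 0.480 | about 100% |
| 0.5 | 0.5 | 0.3 | 0.15 | 30% | 0.350 | 98.1% |

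With b positive, a negative s (referents more deprived) makes D − s × b larger than D, so weighting would then enlarge the gap.

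**Check by simulation.** Inverse probability weights from a logistic propensity model on deprivation alone, in a very large sample:

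- s=0.3, b=0.2: unweighted gap 0.282, weighted 0.223.
- s=0.5, b=0.3: unweighted 0.288, weighted 0.138.
- Total gap 0.09 running wholly through deprivation (s=0.3, b=0.3): unweighted 0.090, weighted 0.002.

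The amounts removed (0.059, 0.150 and 0.088) agree with s × b (0.06, 0.15 and 0.09). A further simulation at 400:200 with s=0.5 and b=0.2 (1,500 runs, robust standard errors) gave a mean estimate of 0.181 and rejection in 52% of runs. That is slightly below the 55.1% in the table, as some loss of precision from weighting would lead one to expect.

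**The case against.** The case for keeping deprivation in the weights is a serious one. Both samples are convenience samples, reached by different routes: section 2.4.1 recruits a self-selecting group through partner organisations, with targeted sampling if needed, while section 2.4.2 recruits referents by local advertisement and social media. A deprivation difference between two such samples may be largely an artefact of recruitment, and the logic model in Appendix 1 describes the referent group as matched. A contrast without deprivation in the weights would carry that artefact, so it is no more certain to recover the population gap. This stands, and it is why the deprivation-weighted estimate should be kept.

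The descriptive analysis also stands as a mitigation. Raw levels in both groups will be shown, so the total gap is not hidden. It is, however, untested and not adjusted for age, sex, ethnicity or region.

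A reader might go further and infer that people with intellectual disabilities live in more deprived areas, so that the plan will understate inequality. The protocol does not say so. Section 3.1 speaks only of varying levels of deprivation, section 2.7 lists several kinds of home without frequencies, and section 1.2 names influences on inclusion without saying that disability leads to area deprivation. A postcode index also picks up personal finances or type of residence only as far as these track the area. Nor do the documents show that the contrast without deprivation is the one correct measure of inequality; that is a choice of estimand.

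Section 2.4.2 defers detail to a later SAP, where a second set of weights could well appear. The point does not rest on its absence. It rests on the protocol fixing a weight set whose estimand differs from the stated aim, without saying so.

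**Conclusion.** The point holds as a mismatch between aim and estimand. The aims ask for the level of inequality, and the one inferential comparison gives the gap at equal area deprivation, unlabelled. Whether this changes the answer depends on two things that the protocol does not supply: how far the recruited groups differ in deprivation, and how strongly deprivation relates to participation.

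Under the assumed ranges the consequence runs from minor to substantial when the true gap is near the detectable 0.2812 SD. That value is the difference which the sample can detect, not an expected gap, so it is the point at which power is most sensitive. With a gap of 0.5 SD, significance is not in doubt and the issue is only the size of the reported estimate. The documents do not establish that the analysis is biased or that inequality will be understated. This is an inexpensive improvement worth making, not a flaw that invalidates the comparison.

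**What to change.** In section 2.4.2, prespecify the group contrast twice from the same data:

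- (a) weighted on region, sex, age band and ethnicity, labelled as the overall gap between the groups;
- (b) with deprivation index added to those four, labelled as the gap remaining at equal area deprivation.

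Report both together, and do not give (b) alone as the level of digital health inequality. If direct adjustment replaces the weights, apply the same pair of covariate sets.

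The cost is one more set of weights and one more row in the results; the planned weights already need every variable. The drawback is that (a) carries any deprivation imbalance produced by how the two convenience samples were recruited. The two estimates should therefore stand side by side with that caveat, and the difference between them should not be read as a clean measure of what deprivation causes.

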Descriptive analysis of levels and frequency of digital health participation. A cross-lagged path analysis (CLPM) will investigate changes over time and identify causal relationships between aspects of digital health participation and physical and mental wellbeing, while controlling for demographic and background characteristics (Kenny & Harackiewicz, 1979). By fitting the model with causal crossed lagged pathways in both directions, we can address whether aspects of digital health participation causally precedes physical and mental wellbeing or vice versa in individuals with intellectual disabilities. Sample sizes $N=100 - 400$ are sufficient for structural equation modelling; more specifically, $N=150$ for models including seven or fewer variables with modest communalities (below 0.5) and zero under identified constructs (Hair *et al.*, 2014). We will fit models with and without cross lagged effects and use likelihood ratio tests (specifically, AIC and BIC criterion) to compare these nested models to determine which better fits the data (Kenny & Harackiewicz, 1979). If data is found to be missing at random (MAR), CLPM analyses will default to using full-information maximum likelihood. All models will be reported with robust standard errors and model fit will be evaluated using the comparative fit index (CFI >0.9), Tucker-Lewis Index (TLI >0.9), standard root mean squared residual (SRMR <0.08) and root mean square error of approximation (RMSEA <0.08), (see Wang & Wang, 2012; Hu & Bentler, 1999; Schreiber *et al.*, 2006).

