We will test whether the data is missing completely at random (MCAR) using Little's test for missing completely-at-random (MAR) (Little, 1988) if more than 10% of data is missing. Data is MCAR if the test is not significant, meaning the estimates will be sufficiently unbiased to not need any adjustments. If data is found to be MAR, GLMs will use multiple imputation via chained equations and up to 10 imputation sets will be generated, then pooled following Rubin's Rules (following Granger *et al.*, 2019). All parameter estimates will be reported with 95% confidence intervals. Both imputed and complete case model estimates will be reported for comparison.

A more detailed Statistical Analysis Plan (SAP) will be developed once WP1 is completed and the digital health participation survey which will be administered as part of WP2 is developed.

2.5 Digital Diary Study of Digital Health Participation (Months 14-16 and 24-32) - Work Package 3 (WP3).

To gain a deeper understanding of how digital health participation operates in the lives of people with intellectual disabilities, WP3 employs principles used in digital ethnographic research. This prioritises prolonged collection of rich, unstructured data through observations and accounts of participants (Hammersely, 2019) in contexts and environments which are predominantly digital (Jensen *et al.*, 2022; Pink *et al.*, 2016). Qualitative digital diaries offer a useful way to explore everyday experiences (Volpe, 2019) by utilising the benefits 'new mobilities' technology offers, enabling the ability to record textual, visual or digital diary information that is located in both time and space (Shellen & Urry, 2006).

We will conduct a digital diary study using tablets housing the ArcGIS software package (Jung & Elwood, 2020), which contains digital storytelling software and story mapping. ArcGIS enables generation of verbal, visual and survey data linked to specific community places. Real-time ArcGIS demographic, verbal, visual and narrative data generation about experiences, thoughts and feelings about using the technology in relation to their health will be gathered from participants, with support and prompting provided weekly by RAs and co-researchers. Concurrent to WP2 accessible 'easy-read' study materials will be developed.

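### The missing-data rule takes a non-significant Little's test as establishing MCAR and makes imputation and FIML wait for a finding of MAR that observed data cannot give, so complete-case estimates can be left biased

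*Protocol*

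**What the plan says.** The rule for the comparative study is in the last part of Protocol section 2.4.2. Missingness is tested "using Little's test for missing completely-at-random (MAR) (Little, 1988) if more than 10% of data is missing"; this wording also attaches the abbreviation MAR to the MCAR test. The consequence of a non-significant result is then fixed: "Data is MCAR if the test is not significant, meaning the estimates will be sufficiently unbiased to not need any adjustments".

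For the other branch the text reads: "If data is found to be MAR, GLMs will use multiple imputation via chained equations and up to 10 imputation sets will be generated". No other test or criterion for MAR is named, and MNAR is not mentioned. The passage adds: "Both imputed and complete case model estimates will be reported for comparison".

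Section 2.4.1 sets a parallel condition for the cross-lagged model (CLPM): "If data is found to be missing at random (MAR), CLPM analyses will default to using full-information maximum likelihood". It does not say what happens if MAR is not found. Section 2.4.2 closes by promising a more detailed SAP once the survey has been developed.

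**The concern.** Two steps of reasoning fail.

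- **Non-significance is read as MCAR.** Little's test compares observed values across missingness patterns. It can lack power, and it cannot see dependence of missingness on the unobserved score itself. It can give evidence against MCAR, never for it.
- **MAR is treated as something that can be found.** MAR and MNAR differ only in how missingness depends on values that were not observed, so no test on the observed data separates them. Both principled methods in the plan depend on a condition that cannot be met.

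Digital health participation is the primary outcome of the comparison. If people with low participation are more likely to have missing scores, the complete cases overstate participation in that group and the estimated inequality shrinks. The rule would then call for no adjustment whenever the test was not significant.

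**Working it through.** **1. The plan's own figure.** Section 2.4.2 states d = 0.2812 at 90% power, alpha 0.05, with 200 referent participants and a 2:1 ratio (so 400 with intellectual disabilities).
- Noncentrality = 0.2812 / √(1/200 + 1/400) = 0.2812 / 0.0866 = 3.247.
- Two-sided normal power = Φ(3.247 − 1.960) = 0.901; the exact noncentral t with 598 df gives 0.900 and a detectable d of 0.2812.
- One-sided testing would give 0.945, so the figure is two-sided. It reproduces, and serves below as the yardstick.

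**2. Power of a test of MCAR (assumed inputs).** Take N = 400 with 12% missing: 48 missing, 352 observed. Suppose the two sets differ by δ SD on one observed variable. Noncentrality λ = δ² × 48 × 352 / 400 = 42.24 δ².

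| δ | λ | 1 variable tested | 5 variables | 10 variables |
|---|---|---|---|---|
| 0.3 | 3.80 | 49% | 28% | 20% |
| 0.5 | 10.56 | 90% | 71% | 57% |
| 1.0 | 42.24 | over 99% | over 99% | over 99% |

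A modest observed difference is usually missed; a large observed one is usually detected.

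**3. The rule applied to simulated data (assumed mechanisms).** 400 + 200 participants, true difference −0.2812 SD, four observed covariates, Little's test at 0.05, 1,500 to 2,000 replicates per scenario. In the outcome-related scenarios, the missing fraction is equal in both groups but depends on low participation only in the group with intellectual disabilities (log-odds slope 0.5 to 1.0 per SD; outcome-covariate correlation 0 to 0.4).

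| Mechanism | Missing | Test non-significant | Complete-case difference in those replicates |
|---|---|---|---|
| True MCAR | 15% | 95% | −0.28 (no bias) |
| MAR, driven by a covariate (slope 0.2 to 0.5, correlation 0.4) | 15% | 44% to 90% | −0.27 to −0.25 unadjusted; about −0.28 adjusted |
| Outcome-related | 15% | 69% to 95% | −0.22 to −0.15 adjusted |
| Outcome-related | 25% | 57% to 96% | −0.18 to −0.07 adjusted |

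Attenuation at 15%: 1 − 0.2201/0.2812 = 22% to 1 − 0.1501/0.2812 = 47%. At 25%: 1 − 0.1826/0.2812 = 35% to 1 − 0.0680/0.2812 = 76%.

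**4. What the test sorts.** With no outcome-covariate correlation and a slope of 0.5 at 15% missing, the adjusted estimate was −0.207 when the test was non-significant and −0.191 when it was significant. The result of the test did not separate less biased data sets from more biased ones.

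**The case against.** Several points on the other side stand.

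- **The dropout figures belong elsewhere.** A reader might apply the 13% and 15% in section 2.4.1 to the group comparison. Those are longitudinal dropout and bear on the CLPM. The comparison is cross-sectional, and no missingness rate is given for it; 15% is only illustrative there. Nor do these figures show that the 10% trigger would go unmet, since they exceed it.
- **Weak test and large bias do not automatically go together.** The bias in one group's mean is the fraction missing times the difference between missing and observed scores. A reader might take 0.10 × 0.5 = 0.05 SD to 0.15 × 1.0 = 0.15 SD, or 18% to 53% of 0.2812, alongside the low power at 0.3 SD. At 0.5 to 1.0 SD the test has 57% to over 99% power if the difference is observed. The two coincide mainly under MNAR, which imputation and FIML alone would not remove.
- **Some inferences go beyond the text.** The protocol nowhere says that a significant test proves MAR; that follows only because no other route is named. It does not say that participants with only a first survey leave the CLPM; it is silent on a fallback. It describes some groups as at risk of digital exclusion, not of non-response, and offers proxy, paper, telephone and face-to-face completion.
- **Replacement of non-completers.** First-survey non-completers may be replaced. They may leave no record to impute, so the fix below would not address that selection.

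Two defences do not hold. The promise to report both imputed and complete-case estimates carries no stated condition, but the non-significant branch calls for no adjustment, so it requires no imputed estimate to compare. Deferral to a SAP does not cure a rule that the protocol already states with its reasoning.

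**Conclusion.** The concern holds for the rule itself: non-significance does not establish MCAR or justify leaving estimates unadjusted, and a finding of MAR cannot be the gate for multiple imputation or FIML. The consequence is that complete-case estimates **can** be biased, not that they will be. There is no such bias under true MCAR, nor under MAR when the drivers of missingness are in a correctly specified model.

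The size cannot be derived from the documents. The attenuation of 22% to 47% at 15% missing, and 35% to 76% at 25%, rests on the assumed outcome-related mechanisms above and shows direction and range only. The documents do not support reading these as expected losses in this study.

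**What to change.** - In section 2.4.2, delete the sentence equating non-significance with MCAR, and remove Little's test with its 10% trigger as a condition for choosing the method. Correct the label that calls the MCAR test MAR. The test may still be reported descriptively.
- In sections 2.4.1 and 2.4.2, delete the condition that MAR be found. Make multiple imputation (GLM) and FIML (CLPM, including participants with only a first survey) the default under a stated MAR assumption.
- Keep the complete-case estimates as the comparison already promised, now reported whatever Little's test shows.
- Add an MNAR sensitivity analysis, because multiple imputation and FIML do not remove MNAR bias.

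The choice of auxiliary variables and the number of imputations can be left to the SAP. The cost is a change of wording and slightly more analysis work; no new data are needed.

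### The comparative analysis caps multiple imputation at 10 sets with no minimum, which leaves avoidable simulation noise in the imputed estimate and its confidence limits (minor)

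*Protocol*

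**What the plan says.** Section 2.4.2 of the protocol treats missing data in the comparative study in steps.

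- Little's test is run "if more than 10% of data is missing".
- If the test is not significant, the data are taken to be missing completely at random and no adjustment is made.
- If the data are instead found to be missing at random, "GLMs will use multiple imputation via chained equations and up to 10 imputation sets will be generated", pooled by Rubin's rules.
- Parameter estimates carry 95% confidence intervals, and "Both imputed and complete case model estimates will be reported for comparison".
- A fuller SAP is promised for after work package 1.

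The text gives no minimum number of sets and does not link the number to the amount of missing data. It does not say whether the imputed or the complete-case estimate governs the conclusion.

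**The concern.** Multiple imputation draws random values, so a pooled estimate from a finite number of sets depends on the seed. The fewer the sets, the larger that dependence. A ceiling of 10 bounds the number on the wrong side: it forbids more sets when more are needed, and it allows 2, 3 or 5.

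The GLM in question estimates the group difference in the primary outcome, which serves the study's main aim of determining digital health inequality. If missing data are appreciable and the result is near the 5% boundary, the imputed estimate could fall on either side of it by the choice of seed. Because the ceiling is written into the protocol, a later SAP that wanted more sets would have to depart from it.

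**Working it through.** **The plan's own figure.** Inputs from section 2.4.2: 200 referent and 400 intellectual-disability participants, 90% power, alpha 0.05, detectable difference d = 0.2812. A two-sided t test with 598 degrees of freedom gives d = 0.28118 at 90% power, so the stated figure reproduces. The complete-data standard error of d is sqrt(1/200 + 1/400) = 0.0866, and the expected test statistic is 0.2812/0.0866 = 3.25.

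**Assumptions.** The fraction of variance due to missing data, λ, is not in the protocol; I take 0.10, 0.20 and 0.30. The calculation is for an unweighted comparison.

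**Simulation error of the pooled estimate.** With m sets and between-imputation variance B, this error is sqrt(B/m). As a share of the standard error with unlimited sets it is sqrt(λ/m).

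| λ | m = 5 | m = 10 | m = 50 |
|---|---|---|---|
| 0.10 | 0.141 | 0.100 | 0.045 |
| 0.20 | 0.200 | 0.141 | 0.063 |
| 0.30 | 0.245 | 0.173 | 0.077 |

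In standardised units at λ = 0.20, the standard error is 0.0866/sqrt(0.8) = 0.0968. Ten sets give a simulation error of 0.141 × 0.0968 = 0.0137, so 95% of seeds put the estimate within ±1.96 × 0.0137 = ±0.027. Fifty sets give 0.063 × 0.0968 = 0.0061, or ±0.012. The confidence limits move with the estimate.

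**Efficiency.** The variance inflation from a finite number of sets is 1 + λ/m. At m = 10 this is 1.01, 1.02 and 1.03, so the standard error grows by only 0.5%, 1.0% and 1.5%.

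**Effect on significance.** P-values were simulated from Rubin's total variance with Barnard-Rubin degrees of freedom (complete-data value 598), two-sided at 5%.

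First, a borderline case: the p-value with unlimited sets is 0.04.

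| λ | p, central 95% of seeds, m = 10 | seeds with p ≥ 0.05, m = 10 | p, central 95% of seeds, m = 50 | seeds with p ≥ 0.05, m = 50 |
|---|---|---|---|---|
| 0.10 | 0.024–0.069 | 25% | 0.032–0.051 | 4% |
| 0.20 | 0.018–0.092 | 36% | 0.028–0.058 | 13% |
| 0.30 | 0.014–0.116 | 43% | 0.026–0.065 | 21% |

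Second, a clear case: if that p-value is 0.01, the share of 10-set runs with p ≥ 0.05 is 0%, 0.2% and 1.7%.

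Third, across studies at the design effect (expected statistic 3.25 × sqrt(1 − λ)), the share in which two independent imputation runs on the same data disagree on significance:

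| λ | m = 10 | m = 50 |
|---|---|---|
| 0.10 | 2.8% | 1.2% |
| 0.20 | 5.3% | 2.2% |
| 0.30 | 8.3% | 3.3% |

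**The case against.** The strongest reply is that little is lost. Ten sets introduce no bias, and Rubin's total variance includes the term (1 + 1/m)B, so the reported interval already allows for the simulation noise. That stands, and nothing here shows the intervals to be invalid.

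Second, the values of λ have no source in the protocol and could be too high. The comparison is cross-sectional, so the 15% dropout allowance for the longitudinal survey does not apply. Section 2.4.1 also provides for replacing participants who do not complete the first survey. At λ = 0.05 the error with 10 sets is sqrt(0.05/10) = 7% of the standard error. This stands as a limit on the size of the effect.

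Third, a complete-case estimate, which needs no seed, is reported alongside. That helps a reader see a divergence, though it does not stabilise the imputed estimate.

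Fourth, the announced SAP can settle the details. That holds for recording the seed and reporting Monte Carlo error, and their absence here is no fault. It does not hold for the ceiling, which the protocol itself fixes.

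Some stronger readings are tempting but not supported:

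- A reader might infer that the 10% threshold switches imputation on and so contributes to the problem. In the text it triggers Little's test, and imputation also needs a finding of missing at random. Where nothing is imputed there is no seed, so the threshold plays no part in the dependence on it.
- A reader might infer that the result would not be reproducible. With a recorded seed a 10-set analysis reproduces exactly; what varies is the answer under another seed.
- A reader might infer that the imputed model alone supplies the primary conclusion. The protocol does not say so, and it states no p-value decision rule for this comparison.

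**Conclusion.** The point holds as a minor one. The protocol fixes an upper limit on the number of imputations where a lower limit is needed. If imputation is used and λ is between 0.10 and 0.30, the seed contributes noise of 10% to 17% of the standard error at the maximum permitted number of sets, and more below it.

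The consequence is mostly confined to borderline results. Averaged over studies at the design effect, moving from 10 to 50 sets lowers disagreement between runs by about 2 to 5 percentage points (2.8% to 1.2% at λ = 0.10; 8.3% to 3.3% at λ = 0.30). These figures rest on the assumed λ, an unweighted comparison and a two-sided 5% criterion. The case for change is that this gain is nearly free, not that the planned analysis is unsound.

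**What to change.** In section 2.4.2, replace the limit of up to 10 sets with a minimum. For example: at least 50 imputation sets, and no fewer than the percentage of participants with any missing analysis variable. Fifty is a practical choice and not a threshold at which the noise vanishes: with λ = 0.20 and p = 0.04 under unlimited sets, 13% of seeds would still give p ≥ 0.05. The second clause raises the number where missing data are extensive.

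The change is one phrase in the protocol, needs no new data, and adds a few minutes of computing for 600 records. It is best made before the data are analysed. The seed and the reporting of Monte Carlo error can be left to the SAP.
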